4.2. Inclusion/Exclusion Criteria

To be eligible for this prospective cohort study subjects must meet **all** of the following criteria:

- i. Incident GEP-NET/Lung NET diagnosis*(see [Appendix A](#))
- ii. Diagnosed 01/01/2019-12/31/2023
- iii. No known prior GEP-NET/Lung NET diagnosis
- iv. Aged ≥ 18 years at diagnosis
- v. At least one site encounter within the study period of January 1, 2019 to December 31, 2023

* See [Appendix A](#) for a full list of International Classification of Diseases, Ninth Revision, Clinical Modification (ICD-9-CM), The International Classification of Diseases, Tenth Revision, Clinical Modification (ICD-10-CM) codes used to define a NET diagnosis. This appendix also lists the ICD-O-3 site codes and eligible histology codes for implementation in tumor registry data sources.

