5.10. Post-consent study procedures

5.10.1. Baseline survey

5.10.1.1. Participation via the NET-PRO PHR

After the subject signs the informed consent document, they will be prompted to create their study account by changing their username and password. Thereafter, they will be invited to complete the first study survey, which will take approximately 40 minutes to complete. This survey asks about current and past health conditions and treatments, symptoms, health behaviors, feelings, concerns, and general preferences about health and health care, physical and mental health, and basic information (like marital status, and height and weight). There are also a few questions to assess comfort with and understanding of health information. Once completed, subjects will be invited to explore the study website which contains a way to view their survey responses, consent document, their study status, and other NET resources.

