6.1. EMR data – Clinical and billing data from the PCORnet CDM

The PCORnet CDM is a key component of the PCORnet Distributed Research Network infrastructure, and will serve as the primary data source for the NET-PRO study. In late 2023, the UICC will request data from sites on all enrolled subjects. Data will include demographics, toxicity outcomes, vitals and vital status, treatments, laboratory tests and results, health conditions (comorbidities), tumor characteristics (from tumor registry variables/tumor tables in the CDM), disease status, and encrypted IDs used to link patient care across sites. The data will cover the period two years prior to the subject's NET diagnosis through approximately 36 months after the date they joined the study. Note, as per the inclusion criteria, we will not be excluding patients who do not have 2 years of look-back data prior to their diagnosis date. Table 2 summarizes the variables that will be obtained from the CDM. The specific code lists for derivation of these variables in the CDM will be later specified and distributed to sites.

Table 2: Patient, clinical and tumor variables that will be measured from the CDM

Concept/variable		CDM Tables
Demographics	Date of birth, sex, Hispanic, Race	Demographic Table
Toxicity outcomes	Acute renal failure, dialysis, liver failure	Diagnosis Table
Vitals	Height, weight, systolic and diastolic blood pressure, smoking	Vitals Table
Cancer Treatments	Somatostatin Analogues (SSAs) (octreotide, lanreotide, pasireotide) Bevacizumab, Cytotoxic chemotherapy, Everolimus, Interferon alpha, Hepatic Artery Bland-, Chemo- or radioembolization, PRRT -Lutetium Lu-177 dotatate, PRRT-Yttrium-90 Dotatoc, Small molecule TKIs, Telotristat ethyl)	Dispensing, prescribing, procedures, and medications administered Tables
Lab values	Alanine transaminase (ALT), Albumin and Microalbumin Albumin/Creatinine and Microalbumin/creatinine Ratio, Alkaline phosphatase (ALP), Aspartate transaminase (AST), AST/ALT ratio, Blood Urea Nitrogen, Chromogranin A, Cystatin C, Hemoglobin, Ki-67, Lymphocytes, Pancreastatin, Serum or Blood Creatinine, Somatostatin, Total Bilirubin	Lab results

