Comorbid conditions	Chronic Pulmonary Disease, Congestive Heart Failure, Coronary Artery Disease, Diabetes with complications, Diabetes without complications, Hypertension, End Stage Renal Disease, Mild Liver Disease, Severe Liver Disease, Peripheral vascular disease, Renal Disease, Myocardial Infarction	Diagnosis Table, Conditions Table (for conditions in the 2 years prior to GEP-NET/lung NET diagnosis)
Vital status	Vital status (death date, cause of death)	Death Table. Death Cause Table – supplemented with local site linkages and patient survey data

Linkage	Patient ID, token	Hash token table (Datavant link module)
Tumor Characteristics	Tumor characteristics (NAACCR required variable list (i.e.: tumor grade, stage, nodal status and other relevant pathological characteristics))	Tumor Table or cancer registry data sources

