6.3. Patient surveys

Table 3 outlines the measures that will be collected from the baseline and follow-up surveys which will be administered through the PHR. The UICC has prepared a data dictionary for the baseline survey. Data dictionaries will also be made available for the follow-up surveys.

Whilst many of the current survey items are derived from validated instruments, or have been used in empirical research studies, we are receiving input from the clinician group and patient advocacy organization committees to adapt and tailor many of these items to a NET population. We anticipate that several physical and psychosocial themes may be missing from the HRQoL questionnaires that we are using which may be important to patients and/or help clinicians in their patient interactions. Therefore, in working with our patient partners and clinician groups we may identify further themes, concepts and items impacting on HRQoL and incorporate these additional measures into the baseline and study follow-up questionnaires.

Table 3: Overview of concepts and measures examined on the baseline and follow-up surveys

Concept/measure	Baseline Survey	Follow-up Surveys
Sociodemographic data (date of birth, sex and gender orientation, race, marital status, ethnicity, state of residence, household income, highest level of educational attainment, health literacy)	X	
Height and weight	X	X
Health Related Quality of Life, QLQ-C30, QLQ-GINET21, Other impacts of cancer (worry, other life events)	X	X
Norfolk Carcinoid Symptom Score [47]	X	X
History of chronic conditions (20-item checklist)[48]	X	
Preferences and attitudes (quality vs quantity of life [49], preferred decision-making role [50, 51], family's role in decision-making)	X	
Attitudes (fatalistic thinking, spirituality) [52], Experiences of care (physician communication, coordination and responsiveness of care [53], actual decision-making role [50]	X	X
Self-reported treatments, including over-the-counter medications and supplements	X	X

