9. STATISTICAL ANALYSIS PLAN

9.1. General Statistical Approach

Continuous variables will be summarized using descriptive statistics such as mean, standard deviation, median, minimum and maximum. Categorical variables will be summarized by count and percentage. Group comparisons will be assessed using chi-squared or Fisher's exact tests for categorical variables, and an analysis of variance or Kruskal-Wallis tests for continuous variables where appropriate. Adjustment for covariates listed in Tables 2 and 3 will be explored for each analysis as needed to account for potential confounding effects. Time-dependent covariates will be incorporated to capture changes in covariates across time, as necessary. Inclusion of random effects to account for potential clustering of patients treated at the same study site will be explored. Depending on the rate and pattern of missing data, multiple imputation methods may be considered to account for data missing at random or attributable to non-ignorable drop-out [56]. Planned study outcomes are summarized in Table 4.

9.1.1. Aim 1

Mixed effects regression models will be utilized to assess changes in HRQoL and symptoms within and between groups (i.e.: different treatment regimens) over time. Random effects will be employed to account for the longitudinally correlated nature of repeated questionnaire measurements. Should completion of questionnaires deviate from the planned assessment time points, a spatial power covariance structure will be included to account for the unequal time spacing between assessments within a patient.

9.1.2. Aim 2

Multinomial logistic regression models will be used to identify which patient, clinical, and tumor characteristics (Table 2), and patient attitudes and beliefs (Table 3) influence selection of treatment regimens for each line of treatment. The conditional Cox regression model proposed by Prentice, Williams, and Peterson (PWP) will be used to simultaneously model the gap times between initial diagnosis and first progression and between subsequent progressions as a function of the prognostic factors of interest for progression-free survival. The baseline hazard is expected to differ for first-line therapy and for subsequent lines of therapy, thus event-specific estimates will be obtained. A robust sandwich estimator will be used to account for potential dependencies within patients. Overall survival will be evaluated using a Cox regression model.

9.1.3. Aim 3

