9.5. Handling missing data

To minimize the effect of missing data on our ability to adjust for confounding factors, any clinical variable found to be insufficiently populated in the CDM upon evaluation of submitted cohort characterization data, will be abstracted via chart review for consented patients. Moreover, all 14 participating sites have agreed to provide tumor characteristics and NAACCR required variables i.e.: tumor grade, stage, nodal status etc.) as important prognostic covariates. This tumor registry data will be populated in each sites CDM tumor tables, and sites will have the opportunity to engage in data quality curation using sample scripts developed by the GPC network informaticists (enhancing future utilization of cancer registry variables in the CDM), see 10.2 below.

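### Aim 2 comorbidity comes from codes in the 2 years before diagnosis, but patients without that look-back are kept, so an absent code cannot be told from an unobserved condition

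*Protocol*

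**What the plan says.** Table 2 (section 6.1) takes the comorbid conditions, among them diabetes, hypertension, and renal, liver and heart disease, from the CDM Diagnosis and Conditions tables, "for conditions in the 2 years prior to GEP-NET/lung NET diagnosis". The text above the table adds that "we will not be excluding patients who do not have 2 years of look-back data prior to their diagnosis date". The only contact criterion in section 4.2 is "At least one site encounter within the study period of January 1, 2019 to December 31, 2023", and that encounter may fall after diagnosis.

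The analysis text then points to this source. Section 9.1.2 takes the patient, clinical and tumor characteristics for the multinomial models from Table 2 and cites Table 3 only for attitudes and beliefs. The synopsis names EMR data as the source for pre-existing comorbidities in Aim 2.

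The protocol also collects other information:

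- **Baseline survey.** Table 3 lists "History of chronic conditions (20-item checklist", and section 5.10.1.1 says "This survey asks about current and past health conditions and treatments".
- **General adjustment rule (9.1).** "Adjustment for covariates listed in Tables 2 and 3 will be explored for each analysis as needed".
- **Chart-review back-up (9.5).** "any clinical variable found to be insufficiently populated in the CDM upon evaluation of submitted cohort characterization data, will be abstracted via chart review".

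No section says how codes, checklist and chart data are combined for comorbidity, or how a patient with no records in the window is classified.

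**The concern.** A variable defined by the presence of a code has two values, code found or code not found. With full look-back, not found is reasonable evidence that the condition is absent. Without look-back it carries almost no information, yet it produces the same value.

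The protocol knows that such patients exist. Appendix B warns that the first cancer code can lag well behind diagnosis when a patient was diagnosed or treated elsewhere, and that patients seen only for a second opinion may not be in the tumor registry. It does not carry this over to comorbidity.

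In Aim 2, cardiovascular, renal and liver disease and diabetes are exposures whose effect on treatment choice is itself the question. Section 9.3 adds a second route, because the Aim 2 models guide which confounders are adjusted for elsewhere. A comorbidity that looks unrelated to treatment because it was poorly captured could be left out of later models. Section 1.1.3 names diabetes and hypertension as risk factors for renal decline after PRRT.

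**Working it through.** The plan states no figure on this point, so there is none to reproduce. The check has two parts.

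**1. Do the stated safeguards reach the problem?**

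- *Chart review (6.2, 9.5).* The trigger is a CDM variable that turns out to be too sparsely filled. A missing creatinine value shows up as an empty field. A missing diagnosis code does not, because it looks like a negative. The examples in 6.2 are laboratory and tumor variables.
- *Checklist.* It is collected at baseline and may be explored as a covariate under 9.1, but the specific Aim 2 sentence does not draw on it.
- *Contrast within Table 2.* The vital-status row states that it is supplemented with site linkages and survey data. Section 7.1 likewise uses self-report to find treatments missed in the EMR. The comorbidity row has no such supplement.

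**2. How large could the effect be?** All inputs here are assumptions. Let p be true prevalence and f the share with no look-back. Assume codes capture nothing in that share and everything in the rest. Observed prevalence is then p(1−f).

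*Look-back differs by treatment group*, with p = 20% in both groups, so the true odds ratio is 1.0:

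- f = 40% v 20%: 0.20×0.60 = 0.12 v 0.20×0.80 = 0.16. OR = (0.12/0.88)/(0.16/0.84) = 0.72.
- f = 30% v 20%: 0.20×0.70 = 0.14 v 0.16. OR = (0.14/0.86)/(0.16/0.84) = 0.85.

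*Look-back does not differ*, with true prevalence 30% v 10%, so the true OR = (0.30/0.70)/(0.10/0.90) = 3.86:

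- f = 10%: (0.27/0.73)/(0.09/0.91) = 3.74
- f = 1/3: (0.20/0.80)/(0.0667/0.9333) = 3.50
- f = 50%: (0.15/0.85)/(0.05/0.95) = 3.35

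Equal loss therefore attenuates only modestly. Unequal loss can create an association where there is none.

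*How much the checklist recovers.* The share of code-free patients who have the condition is pf/(1−p(1−f)). At p = 20% and f = 1/3 this is 0.0667/0.8667 = 7.7%. Suppose a code or a self-report counts as present, and self-report has sensitivity s. The share becomes pf(1−s)/(1−p(1−f)−pfs):

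- s = 0.6: 0.0267/0.8267 = 3.2%
- s = 0.9: 0.0067/0.8067 = 0.8%

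Over p = 10-40% and f = 10-50%, the codes-only figure runs from 1.1% to 25.0%. With the checklist it runs from 0.1% to 11.8%. The value f = 1/3 is only loosely anchored: Appendix B reports that about two-thirds of eligible cases at one site are in its tumor registry, which is not a measure of look-back.

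**The case against.** A reader might infer more than the documents support, in three ways.

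- **That comorbidity is read only from codes.** It is not. The checklist and chart review exist, and 9.1 admits Table 3 covariates to adjustment in every aim.
- **That patients without look-back are scored as disease-free.** No section says so. Section 6.1 defers the code lists, 9.1 allows multiple imputation, 9.3 says the analysis plan will be refined, and an SAP not seen here may settle the classification. What can be said is that the Table 2 variable by itself cannot separate the two states.
- **That the Aim 3 renal comparison is confounded because PRRT patients are more often referred.** The Aim 3 comparators in 8.3 and 9.1.3 all lie within PRRT-treated patients, and the power case in 9.2.3 is within-subject change. A gap in look-back between PRRT and other patients does not confound those contrasts. Nothing in the protocol shows that look-back differs between PRRT regimens.

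The numbers are also a worst case. They assume zero capture without look-back and no help from the cross-site linkage tokens in Table 2 or the site random effects in 9.4. The link from referral to missing look-back to PRRT use is plausible but undocumented. Section 9.2.2 calls the Aim 2 analyses exploratory, and keeping these patients is an open and defensible choice.

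All of this limits the claim, but part of it remains. The protocol itself fixes the window, waives the look-back and names Table 2 as the Aim 2 source. Followed as written, that gives a misclassified exposure. Linkage helps only where a linked site holds the earlier records, and random effects do not correct patient-level misclassification within a site.

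**Conclusion.** The concern holds for Aim 2. The comorbidity variables that the treatment-selection model is told to use cannot distinguish absent from unobserved in patients without look-back, and the stated chart-review trigger may not reveal it. Under-recording is likely. Associations with treatment choice would be somewhat attenuated if look-back is equally missing across treatments, and distorted if it is not (a true odds ratio of 1.0 seen as 0.72 to 0.85 under the assumed figures). The actual size is unknown, because the protocol gives neither the share without look-back nor its relation to treatment.

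For Aim 3 the conclusion is weaker. Adjustment may suffer because confounder choice is guided by the Aim 2 models, but no specific confounding of the PRRT regimen comparisons is shown. The change should be made, since the data that would largely repair the variable are already collected or planned.

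**What to change.** Amend 6.1/Table 2 and 9.1.2 as follows:

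1. Derive a look-back flag: any site encounter in the 2 years before the index date, apart from the diagnostic work-up. Report its frequency by treatment and site.
2. Where the flag is negative, set code-based comorbidity to unknown, not absent.
3. Supplement it from the Survey #1 chronic-condition checklist and from a comorbidity item in the planned chart review, as Table 2 already does with survey data for vital status. State the order of precedence among sources.
4. Multiply impute what remains unknown.
5. Repeat the Aim 2 models, and the adjusted Aim 3 models, in patients with look-back as a sensitivity analysis.

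The cost is protocol and SAP wording, one derived variable and one chart-review item. The downside is small. The checklist is self-reported and completed after diagnosis, so some later-onset conditions may be counted. Its 20 items are not listed in the protocol, so their match to the Table 2 conditions needs checking.

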PRRT represents a true breakthrough in treatment of NETs but many questions remain about sequencing of PRRT with other therapies. PRRT is a form of molecularly targeted therapy, the main goal of which is to selectively deliver a high dose of radiation to the tumor cells, thus limiting irradiation of normal tissues. Unfortunately, due to tubular reabsorption and intracellular trapping of the radionuclide, PRRT therapies can accumulate in the renal cortex inducing toxicity [30]. Proper kidney protection, with the co-infusion of positively charged amino acids, is mandatory. Whilst the radiation dose to the kidneys can be reduced with this pre-treatment, the kidney remains a dose limiting organ

[31] with a creatinine clearance loss of about 3.8% per year for ¹⁷⁷Lu-octreotate and 7.3% per year for ⁹⁰Y-DOTATOC [32]. Moreover, studies have demonstrated a higher and more persistent decline in creatinine clearance if risk factors for delayed renal toxicity are present, particularly long-standing and poorly controlled diabetes and hypertension [33, 34]. On January 26, 2018, the US Food and Drug Administration (FDA) approved Lutathera (¹⁷⁷Lu-DOTATATE), a radiolabeled somatostatin analog, for the treatment of adults with somatostatin receptor-positive GEP-NETs [35]. Lutathera, is the first radiopharmaceutical to be approved by the FDA for this patient population. We are likely to see an increase in the use of ¹⁷⁷Lu-DOTATATE outside specialist NET centers. Therefore, real-world data on variables that may influence patient reported outcomes (i.e.: toxicities and adverse effects) and risk of progression after PRRT in combination with other biological therapies, is much needed.

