- 5) **Adverse toxicities.** We will assess incident acute renal failure, dialysis and liver failure during study follow-up (from diagnosis codes in the CDM). The occurrence of these events will be compared in reference to the treatment regimens received.
[Time Frame: Up to 5 years]

Table 4: Overview of Primary and Secondary outcomes for NET-PRO by project aims

Primary or Secondary	Name of Outcome	Specific Measure(s)/ Instrument(s) to Be Used	Timepoints (mths)	PROMIS and/or Core Outcome Set ?	Powered Yes/No/NA
Aim 1					
Primary	Health related Quality of Life (HRQoL)	EORTC QLQ-C30 EORTC QLQ-GI.NET21	0, 6, 12, 18	Yes	Yes
Secondary	Symptom inventory	Norfolk Carcinoid Symptom Score [49] Norfolk Carcinoid Symptom Score [49]	0, 6, 12, 18	No	No
Secondary	Experiences of care	Physician communication, coordination and responsiveness of care [62]	0, 6, 12, 18	No	No
Aim 2					
Primary	Sequencing of treatment regimens	-	0-60	No	Yes
Secondary	Progression-free survival	Time to event (Categorization of stable disease, disease progression with no change in treatment, disease progression with changes in treatment, and indeterminate)	0-60	No	Yes
Secondary	Overall survival	Time to event	0-60	No	NA
Secondary	Adverse toxicities	Incident acute renal failure, dialysis and liver failure during follow-up	0-60	No	NA
Aim 3					
Primary	Renal function	Creatinine clearance loss (per/Yr)	0, 6, 12, 18	No	Yes
Secondary	Adverse toxicities	CDM diagnosis codes for acute renal failure, dialysis and liver failure during follow-up	Up to 60	No	No
Secondary	Health related Quality of Life (HRQoL)	Changes in HRQoL and symptom scores	0, 6, 12, 18	No	No
Secondary	Renal toxicity (creatinine clearance) by PRRT isotope	Creatinine clearance loss (per/Yr) 177Lu vs 90Y	Up to 60	No	No
Secondary	Renal toxicity of PRRT by primary tumor location & grade 3 disease	Creatinine clearance loss (per/Yr) GEP-NETs vs lung NETs and G3	Up to 60	No	No

NA: Not applicable

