The validity of each computable phenotype is also discussed. Where available, results from validation studies performed at the University of Iowa Coordinating Center (UICC) are provided. Each site is encouraged to conduct its own validation studies, and the UICC can provide assistance for this based on its experience.

It is useful to remember that prospective enrollees will confirm their eligibility by responding to eligibility questions early in the enrollment process. This will serve as a final check in case the phenotype mistakenly identifies someone as having a qualifying NET. The recruiting materials have been worded carefully to minimize the possibility that a potential enrollee is alarmed to be contacted for a study focused on NETs.

Following the ADAPTABLE example, the UICC will continue to develop and refine these computable phenotypes to maximize their performance. This will happen through the life of the project.

Phenotypes that use diagnosis codes in electronic health record (EHR) data (research warehouse or CDM)

Many research institutions maintain medical record and billing data in a clinical research data warehouse (CRDW) that contains structured information on diagnoses and procedures. The PCORnet Common Data Model (CDM) is often populated by this source data. Computable phenotypes can be applied to the CDM or the underlying CRDW (which may be updated more frequently than the CDM).

An advantage of CRDW data is that patient data are structured by clinical or billing staff in real-world settings using the International Classification of Diseases (ICD) system (9th and 10th editions). While data are generally high quality, errors can occur. Also, diagnoses can change or be refined over time, and these changes are not always clearly documented. Some ICD codes are ambiguous with regard to tumor site (see the ICD codes labeled AMBIGUOUS in the Appendix). It is also important to note that the date a cancer ICD diagnosis code first appears on an encounter cannot necessarily be considered to be the date of cancer diagnosis; it generally lags behind the true diagnosis date. That lag in time can be substantial, especially if a patient was originally diagnosed or treated at another institution.

Phenotype for low-touch recruitment (without prior chart review or clinic visit): ‘High positive predictive value phenotype’

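### Coded toxicities are called incident, but no rule excludes prior disease, and the Diagnosis-Table-only source misses procedure-coded dialysis and new ESRD without a dialysis code

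*Protocol*

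**What the plan says.** Protocol section 7.2 item 5 defines the secondary toxicity outcome: "We will assess incident acute renal failure, dialysis and liver failure during study follow-up (from diagnosis codes in the CDM"). It adds: "The occurrence of these events will be compared in reference to the treatment regimens received". Table 4 lists the outcome as secondary under Aim 2 (power entry NA) and under Aim 3 (power entry No).

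Table 2 in section 6.1 fixes the source. The toxicity row reads "Acute renal failure, dialysis, liver failure" and names only the Diagnosis Table. ESRD and severe liver disease sit in a different row, as comorbid conditions ("End Stage Renal Disease, Mild Liver Disease, Severe Liver Disease"), and that row covers only the two years before the NET diagnosis. Section 6.1 leaves the code lists to be specified later.

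On prior history, section 6.1 says "we will not be excluding patients who do not have 2 years of look-back data prior to their diagnosis date". The only encounter requirement in section 4.2 is "At least one site encounter within the study period of January 1, 2019 to December 31, 2023", so no record before diagnosis is needed.

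**The concern.** An event is incident only if the patient was free of the condition beforehand. For a patient with no records before diagnosis, the CDM cannot show this, and the protocol does not say how such a patient is handled. For a chronic state such as maintenance dialysis, the first local code may mark arrival at the site rather than onset.

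The source rule also works the other way. New events that never appear as one of the three listed diagnosis concepts are not counted.

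At stake is a between-regimen safety comparison that could mix pre-existing disease with an incomplete count of new disease. The two errors have opposite signs, and nothing ensures that they cancel or that they are equal across regimens.

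**Working it through.** The protocol gives no event rate, sample size or power for this outcome, so there is no figure to reproduce. The check has two parts.

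**1. Applying the rules as written**

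- *Maintenance dialysis or chronic liver failure before the NET, no look-back at the site.* The first local code falls after the index date. Nothing in 7.2 item 5 removes it, so it can count as an event. If the CDM is the only source, the comorbidity row for the same patient is empty.
- *Dialysis starts in follow-up and is recorded only as a procedure.* The Diagnosis Table is the sole source in Table 2, so the event is missed. The cancer-treatment row of the same table already draws on procedures.
- *ESRD develops after diagnosis, with no dialysis diagnosis code.* The toxicity row does not list ESRD and the comorbidity window has closed, so this outcome misses it.
- *ESRD develops after diagnosis, with a dialysis diagnosis code.* It is counted.
- *Acute renal failure.* This is a new episode by definition, so the first problem does not reach it.

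Section 7.1 item 4 separately measures creatinine clearance around PRRT cycles to the end of follow-up. That covers renal decline where creatinine is available. It does not cover liver failure, and it is framed around PRRT rather than the other regimens in Aim 2.

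**2. Scale of the false-event side, on assumed inputs**

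None of these inputs is in the documents:

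- f, share without look-back: 10% to 50%
- p, prevalence of pre-existing dialysis or liver failure: 0.5% to 2%
- i, true incidence among those free of the condition: 1% to 3%

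Worst case: every pre-existing case without look-back is first coded in follow-up and none is screened out. Those with look-back are recognized and not counted.

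Apparent risk = i(1 − p) + f·p. False share = f·p / [i(1 − p) + f·p].

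- Low end (f = 10%, p = 0.5%, i = 3%): 0.0005 / (0.02985 + 0.0005) = 1.6%.
- High end (f = 50%, p = 2%, i = 1%): 0.0100 / (0.0098 + 0.0100) = 50.5%.
- False events among the 3,010 patients of section 9.2: 3,010 × 0.0005 = 1.5, up to 3,010 × 0.0100 = 30.1.

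Now suppose 60% of one regimen group and 20% of another lack look-back, with no true difference. The apparent risk ratio is [i(1 − p) + 0.6p] / [i(1 − p) + 0.2p].

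- p = 0.5%, i = 3%: 0.03285 / 0.03085 = 1.06.
- p = 2%, i = 1%: 0.0218 / 0.0138 = 1.58.

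For a PRRT group of 0.10 × 3,010 = 301 patients at f = 60%, false events run from 301 × 0.6 × 0.005 = 0.9 to 301 × 0.6 × 0.02 = 3.6. True events run from 301 × 0.01 × 0.98 = 2.9 to 301 × 0.03 × 0.995 = 9.0. The counts are small on both sides, so a few misclassified patients can matter.

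The missed-event side cannot be sized, because nothing is stated about how sites record dialysis or ESRD.

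**The case against.** The best reply is that the word incident already implies freedom from prior disease, that code lists are deferred, and that a washout rule is ordinary SAP detail. Keeping patients without look-back is disclosed and reasonable. Prior disease may also surface elsewhere: the 20-item chronic-condition checklist in the baseline survey (Table 3), encrypted IDs linking care across sites (section 6.1), and chart review of variables poorly populated in the CDM (sections 6.2 and 9.5). The outcome is secondary and unpowered.

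Much of this stands. Retaining these patients is not an error, and the definition of incident taken alone would be largely a matter for the SAP. What remains is that the protocol itself fixes the source table, the event list and the comorbidity window, and followed as written these lose events. The safeguards exist but none is tied to this outcome. The checklist is completed at enrollment, which may come years after a 2019 diagnosis (section 11 projects the first enrollment for April 2022), and no onset dating is described. A missing diagnosis code looks like absence of disease, so it may not trigger chart review.

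A reader might infer several stronger things that the documents do not support:

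- *That pre-existing disease will be counted.* It can be; the deferred code lists and the safeguards could catch some of it.
- *That new ESRD is ignored altogether.* ESRD with a dialysis diagnosis code counts here, and renal decline is Aim 3's primary outcome. The gradual harm described in section 1.1.3 ("a higher and more persistent decline in creatinine clearance if risk factors for delayed renal toxicity are present") is what that primary outcome addresses.
- *That Appendix B documents the coding lag for renal or liver disease.* Its warning ("That lag in time can be substantial, especially if a patient was originally diagnosed or treated at another institution") concerns the first cancer code. Extending it to organ-failure codes is plausible, but it is an inference.
- *That the bias runs against PRRT.* No document gives look-back completeness by regimen.

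**Conclusion.** The point holds as a limited defect in a secondary outcome. As written, pre-existing maintenance dialysis or chronic liver failure can be counted as an incident toxicity, while procedure-only dialysis and new ESRD without a dialysis diagnosis code are missed. The missed-event part follows directly from Table 2. The false-event part rests on the absence of any stated prior-event exclusion and on some pre-existing cases being first coded locally during follow-up.

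The size cannot be derived from the documents. The ranges above (false share 1.6% to 50.5%; risk ratio 1.06 to 1.58 under unequal look-back) depend wholly on assumed inputs and a worst-case mechanism. They show only that the bias could be negligible or material. The primary outcomes are not affected.

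**What to change.** In Table 2 and section 7.2 item 5:

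1. Take dialysis from the Procedures Table as well as the Diagnosis Table, and count post-diagnosis ESRD codes as events.
2. For each condition, exclude from the at-risk set any patient with evidence of that condition before regimen start, drawn from available look-back codes, the baseline checklist, linked records or the planned chart review. A checklist entry does not date onset, so date it from the chart.
3. Add a sensitivity analysis restricted to patients with look-back, and report events in the others as onset unknown.

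Eligibility and the cohort stay as they are. The cost is protocol wording, a few more codes, and some onset checks within the chart abstraction already planned for every subject. The downside is a somewhat smaller at-risk set for an outcome that is not powered in any case.
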